## 7.0 SAFETY REPORTING

Salix maintains a robust pharmacovigilance system comprised of a governance framework and standard operating procedures supporting a systematic process for review, evaluation, and management of accumulating safety data from clinical trials and other sources to:

- Identify a potential new safety signal;
- Ensure that an investigational product's risks are adequately assessed and communicated to investigators, IRBs/IECs, and regulatory bodies during clinical development.
- For this study, safety monitoring activities will include but are not limited to:
- Review and evaluation of single SAE occurrences in real-time as reported through the SAE reporting process as outlined in this section of the protocol;
- Review and evaluation, in real-time, of one or more occurrences of an uncommon SAE that is not commonly associated with product exposure;
- Findings and/or safety data obtained during this study will provide information for the overall review of safety that is conducted by Salix on a routine basis. Salix will report expeditiously any findings from clinical trials (ongoing or completed), epidemiological studies, pooled analysis of multiple studies, and findings from animal or in vitro testing that suggest a significant risk in humans exposed to the study product.

Safety data collection for this study begins at the time of the subject's signing of the informed consent according to the operating definitions defined in this section of the protocol. The investigator is responsible for the detection and documentation of events that meet the definition of an unanticipated problem (refer to the protocol Section 10.1), AE or SAE.

### 7.1 Operating Definitions for Assessing Safety

#### 7.1.1 Adverse Event

An AE is any untoward medical occurrence in a subject or clinical investigation subject administered a study product and which does not necessarily have a causal relationship with the treatment.

An AE can therefore be any unfavorable and unintended sign (that could include a clinically significant abnormal laboratory finding), symptom, or disease temporally associated with the use of a study product, without any judgment about causality (i.e., whether or not considered related to the study product).

An AE does include the following:

Confidential

---

- Exacerbation or worsening of a pre-existing illness. NOTE: if the pre-existing illness is the disease under study, then “exacerbation” refers to an unexpected worsening from the condition at baseline.
- Increase in frequency or intensity of a pre-existing episodic event or condition.
- Condition detected or diagnosed after study product administration even though it may have been present prior to the start of the study.
- Symptom associated with disease not previously reported by the subject.

An AE does not include the following:

- Medical or surgical procedures (e.g., surgery, endoscopy, tooth extraction, transfusion) as event terms; the condition that led to the procedure is the AE if it meets the definition of an AE.
- Situations where an untoward medical occurrence has not occurred (e.g., hospitalization for cosmetic elective surgery; and social and/or convenience admissions).
- Overdose of either study product or concurrent medication without any signs or symptoms.
- Symptoms associated with disease, which are consistent with the subject’s usual clinical course; unless the subject experiences worsening of their symptom(s) or the symptom(s) meet the criteria for an SAE.

#### 7.1.2 Serious Adverse Event

A SAE is any AE, occurring at any dose, which results in any of the following outcomes (“Occurring at any dose” does not imply that the subject received study product):

- Results in death
- Is life threatening

**NOTE:** Life-threatening means that the subject was, in the view of the investigator or sponsor, at immediate risk of death at the time of the event. This definition does not refer to an event which hypothetically might have caused death if it were more severe.

- Requires inpatient hospitalization or prolongation of existing hospitalization

**NOTE:** Complications that occur during hospitalization are AEs. If a complication prolongs hospitalization or fulfills any other serious criteria, the event is serious.

Hospitalization for elective treatment of a pre-existing condition that did not worsen from baseline is not considered to be an AE. “In-patient” hospitalization means the subject has been formally admitted to a hospital for medical reasons. This may or may not be overnight. It does not include presentation at a casualty or emergency room.

**Confidential**

---

- A persistent or significant incapacity or substantial disruption of the ability to conduct normal life functions.

**NOTE:** The term disability means a substantial disruption of a person's ability to conduct normal life functions. This definition is not intended to include experiences of relatively minor medical significance such as uncomplicated headache, nausea, vomiting, diarrhea, influenza, or accidental trauma (e.g., sprained ankle) that may interfere or prevent everyday life functions but do not constitute a substantial disruption.

- A congenital anomaly or birth defect in the offspring of a subject who received study product.
- Important medical events that do not result in death, are not life-threatening, or require hospitalization may be considered an SAE when, based upon appropriate medical judgment, they may jeopardize the subject and may require medical or surgical intervention to prevent one of the outcomes listed in this definition.

**NOTE:** Examples of such medical events include allergic bronchospasm requiring intensive treatment in an emergency room or at home, blood dyscrasias or convulsions that do not result in inpatient hospitalization, or the development of drug dependency or drug abuse.

Additionally, an adverse event meeting any of the serious outcomes previously defined above that is assessed by the investigator as resulting from study participation (regardless of relationship to study drug) should be treated as a SAE for this protocol (e.g., complications resulting from the taking of a blood sample or performance of a protocol required procedure).

Medical and scientific judgment should be used in deciding whether prompt reporting is appropriate in case of events that do not meet the serious criteria above.

## **7.2 Clinical Laboratory Abnormalities and Other Abnormal Assessments as AEs and SAEs**

Abnormal laboratory findings (e.g., clinical chemistry, hematology, and urinalysis) or other abnormal assessments (e.g., abnormal findings during examinations or ECG monitoring) that are judged by the investigator as **clinically significant** must be recorded as AEs or SAEs if they meet the definition of an AE or SAE. The investigator should exercise his or her medical and scientific judgment in deciding whether an abnormal laboratory finding or other abnormal assessment (including ECG monitoring) is clinically significant.

## **7.3 Method, Frequency, and Time Period for Detecting AEs and SAEs**

At each visit, after the subject has had an opportunity to spontaneously mention any problems, the investigator should inquire about AEs by asking the following standard questions:

**Confidential**

---

1. "Have you had any (other) medical problems since your last visit/assessment?"
2. "Have you taken any new medicines, other than those given to you in this study, since your last visit/assessment?"

### **7.3.1 The Time Period for Detecting and Reporting of AEs and SAEs**

The Time Period for Detecting and Reporting of AEs and SAEs is from the time of informed consent through study completion/withdrawal, including the follow-up period.

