**Confidential**

---

EIR was used in GRACE 01 and 02, and the present formulation was used in RETIC/03/06. GRACE 01 was a placebo controlled study in 83 mild to moderate CD patients that evaluated Rifaximin EIR 800 mg QD and BID versus placebo; GRACE 02 was an uncontrolled study that evaluated Rifaximin EIR 800 mg QD and BID. Efficacy was evaluated primarily by the rate of clinical remission defined as CDAI score < 150 points after 12 weeks of therapy. Given the small number of patients in both studies, and the uncontrolled design of GRACE 02, neither study met the primary endpoint; data did support potential efficacy in the 800 mg BID regimen.

The current tablet formulation of Rifaximin EIR was evaluated in a Phase II dose range finding study in 402 patients with an acute flare of CD (RETIC/03/06). Patients with a CDAI between 220 and 400 points were randomized to 4 treatment groups: Rifaximin EIR 400 mg twice a day, Rifaximin EIR 800 mg BID, Rifaximin EIR 1200 mg BID or placebo BID for 12 weeks. Patients who achieved clinical remission at the end of the treatment period, defined as CDAI score <150 points, were admitted to a 3-month follow-up phase. Patients were allowed to continue stable doses of oral 5-ASA, mercaptopurine, azathioprine, and/or methotrexate as concomitant therapies throughout the study (up to 12 weeks), while the use of antibiotics and oral, intravenous, and rectal steroids was not permitted.

As add-on therapy (83% of enrolled patients were treated with stable doses of 5-ASA and/or methotrexate, azathioprine and mercaptopurine), Rifaximin EIR 800 mg twice a day was statistically superior to placebo in inducing clinical remission (CDAI < 150 points) after 12 weeks of therapy ( $p = 0.007$ ) and maintaining remission for three months after Rifaximin EIR was stopped ( $p = 0.02$ ).

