Headache (6% of patients), CD symptoms (6% of patients), nausea (4% of patients), flatulence (2% of patients), nasopharyngitis (2% of patients), and fever (2% of patients) were the most commonly reported drug-related AEs. One case of *C. difficile* infection was diagnosed 20 days after the end of the treatment period in a patient who received Rifaximin EIR 800 mg twice daily. A sudden death during the follow-up period, caused by acute massive bilateral pulmonary edema, was reported in a patient with preexisting concomitant arrhythmia. The death was assessed as unlikely related to the study drug. No clinically significant changes in the results of safety laboratory tests were observed in any study group.

In addition to the studies noted above for Rifaximin EIR, rifaximin has been studied in approximately 5000 subjects in multiple clinical studies in irritable bowel disease (IBS) (N = 1103); and in other therapeutic areas including treatment of travelers' diarrhea (N = 593), travelers' diarrhea prophylaxis (N = 820), acute hepatic encephalopathy (N = 152), and recurrence of hepatic encephalopathy (N = 348). In addition, there is over 20 years of post-marketing experience with the drug.

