**6.1.6        Visit 16: End of Treatment (EOT) Visit, Week 52/Day 364 (± 3 days)**

The subject's final dose of study drug will be the evening before Visit 16. The following assessments are to be completed at this visit:

- Adverse events and concomitant medications
- Vital signs and weight
- Electrocardiogram
- Full physical examination including disease specific examination (including assessments for abdominal mass and extraintestinal manifestations of Crohn's disease based on CDAI – see Appendix 2).

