### 6.3.3 Stool Sample Collection and Testing

Stool sample collection should be performed for the following visits: Screening, Visit 7, and Visit 16 (EOT). Fresh stool samples will be collected at each of the above visits whenever possible. If the subject cannot produce a sample during the visit, the subject will be issued a collection kit and asked to collect a specimen at home, refrigerate it immediately, and bring it to the clinic as soon as possible. Stool samples will be aliquoted into 2-mL polypropylene cryovials, stored at  $\leq -20^{\circ}\text{C}$  at the clinical site, shipped on dry ice and stored long term at  $\leq -70^{\circ}\text{C}$ . Stool samples will be used for the following:

- **Safety Testing for *C. difficile*:** A stool sample for analysis of *C. difficile* for Toxins A & B will be collected at Screening, Visit 7, and Visit 16. Testing will be performed by enzyme immunoassay (EIA).
  - Stool samples testing positive for *C. difficile* Toxin B will be cultured and tested for resistance to select antibiotics.
- **Fecal Calprotectin Immunoassay:** A stool sample for assay of fecal calprotectin will be collected at Screening, Visit 7, and Visit 16. Stool samples will be collected in sterile specimen cups and stored immediately at  $\leq -20^{\circ}\text{C}$ . Samples will be shipped frozen on dry ice to the central laboratory for testing. Testing will be performed by immunoassay.
- **Microbiota Characterization: Susceptibility Testing:** In a subset of the study population (approximately 10%), the susceptibility of the stool microbiota to rifaximin, rifampin, and other selected antibiotics of clinical interest will be characterized. Stool samples will be inoculated onto various media to identify organisms. Stool cultures will identify and isolate yeast as well as selected bacteria, chosen to incorporate the most prevalent species of intestinal bacteria. Bacteria will be identified and characterized by morphology and physical tests, with identity confirmed with molecular identification systems. Yeast will be identified if present in stool, but will not be tested further. Bacterial sensitivity testing will be performed by broth microdilution (per Clinical Laboratory Standards Institute (CLSI) document M7-A8) for aerobic bacteria and by agar dilution for anaerobic bacteria using clinically relevant antibiotics. Duplicate samples of all isolates and stool aliquots will be stored to allow for potential future analysis.

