#### **6.3.5 Safety Monitoring for *C. difficile***

Stool samples must be collected and tested for *C. difficile* Toxin B gene (tcdB) using real-time polymerase chain reaction (PCR) method for any subject who has worsening, acute diarrhea and abdominal pain during the study, defined by:

- Subject had at least 3 unformed (loose or watery) stools in the last 24 hours.

AND

- Subject has at least 1 other sign of enteric infection present, such as fever, nausea/loss of appetite, vomiting, severe abdominal pain or discomfort.
  - Stool samples testing positive for *C. difficile* Toxin B, will be cultured and tested for resistance to select antibiotics.

All positive test results will be recorded as an adverse event.

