### **7.3.2 Post-Study SAEs**

Investigators are not obligated to actively seek SAE information in former study participants, but investigators are encouraged to notify Salix of any SAEs occurring at any time after a subject has discontinued or terminated study participation that they judge may reasonably be related to study treatment or study participation.

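### Post-treatment C. difficile: collection usually ends before the 20-day delay of the Phase 2 case, and the SAP's 5-day rule leaves non-fatal events that are collected out of every by-arm AE table

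*Protocol*

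**What the plan says.** **Background.** Protocol 1.4 describes the Phase 2 dose-ranging study. Of C. difficile it says that one "infection was diagnosed 20 days after the end of the treatment period in a patient who received Rifaximin EIR 800 mg twice daily". Patients in remission at the end of that study's 12 weeks "were admitted to a 3-month follow-up phase".

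**Testing here.** Several enteric pathogens are screened for at entry, but C. difficile is the only one tested for by name after that. Protocol 6.3.3 schedules a toxin immunoassay at Screening, Visit 7 and Visit 16. Protocol 6.3.5 requires a toxin-gene PCR whenever symptoms meet stated criteria during the study, and adds: "All positive test results will be recorded as an adverse event".

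**Collection.** Protocol 6.1.6 states: "The subject's final dose of study drug will be the evening before Visit 16". Visit 17, the end-of-study visit, is on Day 378 ± 3. Protocol 7.3.1 says that the AE and SAE period "is from the time of informed consent through study completion/withdrawal, including the follow-up period". After that, Protocol 7.3.2 says: "Investigators are not obligated to actively seek SAE information in former study participants". It does encourage voluntary notification of SAEs judged possibly related. Protocol 4.5 asks for an attempt at 14 days of follow-up after early discontinuation of study drug. Where the stop was for an AE or SAE, follow-up is at least 14 days or until the condition resolves or stabilizes.

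**Tabulation.** Protocol 8.6.5 and SAP 7.8.3 define a treatment-emergent AE as one starting, or worsening, from Day 1 on, with no end date. SAP 7.8.3.1 gives a second rule: a non-fatal AE must start no later than 5 days after the last dose, and a fatal one no later than 30 days. Every AE summary listed in SAP 7.8.3 is of treatment-emergent events, by body system and preferred term.

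**The concern.** C. difficile is the infection the protocol watches most closely, and exposure here is up to 52 weeks against 12 weeks in Phase 2. The one case the protocol reports was found after treatment, so the post-treatment period is where a careful reader would look. Two things weaken that view.

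- Mandatory collection usually closes before the delay seen in Phase 2.
- The SAP's narrower rule then removes most of the post-treatment period that is collected from the comparative tables. It does so inside a section whose opening paragraph still carries the open-ended definition.

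At stake is how far a statement about C. difficile by arm can be trusted. A low count could partly reflect the window and the table layout, and the clinical study report would contain no single table from which to tell.

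**Working it through.** **The plan's own figures.** End of treatment is Day 364 and end of study is Day 378: 378 − 364 = 14 days, the stated 2-week follow-up. Maximum participation is 3 + 52 + 2 = 57 weeks, as the synopsis states. The schedule is internally consistent.

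**Collection after the last dose.** The last dose is the evening before Visit 16, so nominally Day 363.
- Nominal: 378 − 363 = 15 days.
- Windows: Visit 16 on Days 361 to 367 puts the last dose on Days 360 to 366. Visit 17 falls on Days 375 to 381. Shortest gap: 375 − 366 = 9 days. Longest gap: 381 − 360 = 21 days.
- Of the 7 × 7 = 49 combinations of visit days, 3 reach 20 days or more (gap = 15 + shift of Visit 17 − shift of Visit 16, so the difference in shifts must be at least 5). This is a count of combinations, not a probability.
- Early stop: an attempted 14 days.

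**Against the Phase 2 timing.** Taking its end of treatment as the last dose, day 20 is study Day 363 + 20 = 383.
- Past nominal end of study: 383 − 378 = 5 days.
- Past the 14-day follow-up: 20 − 14 = 6 days.
- Past the SAP's non-fatal cut-off: 20 − 5 = 15 days.

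**Collected but not tabulated, under SAP 7.8.3.1.**

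| Route | Days collected after last dose | Days beyond the +5 cut-off |
|---|---|---|
| Nominal completer | 15 | 15 − 5 = 10 (days 6 to 15) |
| Shortest window | 9 | 9 − 5 = 4 |
| Longest window | 21 | 21 − 5 = 16 |
| Early stop | 14 | 14 − 5 = 9 (days 6 to 14) |

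At nominal timing, 10 of the 15 collected post-dose days do not count for non-fatal events. Because the SAE summary is also restricted to treatment-emergent events, a serious non-fatal case in those days drops out of that table too.

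**Definitions side by side.** Protocol 8.6.5: no end date. SAP 7.8.3: same wording, no end date. SAP 7.8.3.1: last dose + 5 days (non-fatal) or + 30 days (fatal). SAP section 8, on changes from protocol-specified analyses, does not mention a narrower treatment-emergent window. An event on day 10 is therefore treatment-emergent under two of the three passages and not under the third.

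**C. difficile in the analysis sections.** Protocol 8.6.3 to 8.6.10 and SAP 7.8 contain no table specific to C. difficile. The instruction to record positives as AEs stands in Protocol 6.3.5, on symptom-triggered PCR. Protocol 6.3.3 has no such sentence for the scheduled immunoassay, so it is unclear whether an asymptomatic positive becomes an AE.

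**The case against.** A reader might infer that an event like the Phase 2 case would simply go unreported. The documents do not support that.

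- Protocol 1.4 gives a diagnosis date only, with no symptom onset and no seriousness. AE windows run on start date, so if symptoms began earlier the case could fall inside collection.
- Protocol 7.5 requires every AE to be followed to resolution, stabilization or explanation, so symptoms recorded before Visit 17 could lead to a later diagnosis that is captured.
- Serious, possibly related cases can still be notified under Protocol 7.3.2, though only voluntarily.
- Stops due to an AE may be followed beyond 14 days, and the visit windows can reach 21.
- Symptom-triggered PCR applies throughout the study. Appendix 1, note b, includes it in the safety laboratory tests, which Visit 17 has.

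Nor is it right that C. difficile results would be invisible. Symptomatic positives become AE rows if treatment-emergent, SAP 7.1 lists all data by subject, and SAP 7.8.4 summarizes laboratory values by time point. The same window also applies in both arms.

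All of this stands, and it limits the collection half to new, non-serious events. It does not answer the analysis half. Listings are not a by-arm comparison. A by-visit laboratory summary that does not name C. difficile gives no count of affected subjects. The conflict between SAP 7.8.3 and 7.8.3.1 is on the page whichever rule was intended.

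**Conclusion.** The point holds in two parts of unequal weight.

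1. **Analysis (stronger).** The SAP carries two incompatible treatment-emergent definitions. The narrower one departs from the protocol without being listed as a change. Applied as written, it leaves non-fatal C. difficile AEs starting on about days 6 to 15 after the last dose out of every by-arm AE table although they are collected, and no dedicated summary makes up for it.
2. **Collection (weaker).** A new, non-serious event arising about 20 days after the last dose would usually fall outside mandatory collection: 5 days beyond at nominal timing, and inside it in only 3 of 49 window combinations. This assumes that the 20 days runs from the last dose and that onset is near diagnosis; the protocol states neither.

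It would be tempting to scale the single case to the planned 330 subjects per arm and quote an expected number missed. The documents do not allow it: Phase 2 arm sizes are not given, one case carries almost no information on a rate, and SAP 7.3 says that both studies will be terminated early. No expected count is offered, and the point does not need one.

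**What to change.** 1. **Reconcile the treatment-emergent definitions** in SAP 7.8.3 and 7.8.3.1 with each other and with Protocol 8.6.5. If a limit after the last dose is kept, list it in SAP section 8 with the reason.
2. **Add one by-arm table to SAP 7.8.3**: subjects with any C. difficile event after first dose. Count AE terms, scheduled immunoassay positives, symptom-triggered PCR positives, and any post-study SAE reports held in the safety database (SAP 7.8.3.4 already reconciles that database with the clinical one). Count each subject once, split on-treatment from post-treatment, and do not restrict the table to the treatment-emergent window.
3. **Ask the sponsor to reconcile** the follow-up and reporting period in Protocol 7.3.1 and 7.3.2 with the timing of the case in Protocol 1.4, and to state its reasoning. No particular period is proposed here.

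Items 1 and 2 use data already held, so they remain practical with early termination and an abbreviated report. The cost is a wording change and one extra table, and possibly a few more events shown.
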